10.2.2. Adverse Drug Reaction

All noxious and unintended responses to a medicinal product related to any dose should be considered an ADR. “Responses” to a medicinal product means that a causal relationship

between a medicinal product and an AE is at least a reasonable possibility (ie, the relationship cannot be ruled out).

An unexpected ADR is defined as an adverse reaction, the nature or severity of which is not consistent with the applicable product information (eg, IB for an unapproved investigational product or package insert/summary of product characteristics for an approved product).

10.2.3. Reporting

All AEs occurring during the course of the study (starting from signing informed consent to study completion or discontinuation) will be collected on the AE eCRF. Patients should be instructed to report any AE that they experience to the Investigator through 30 days following the last dose of study drug. Beginning with Visit S2 (Week -4), Investigators should make an assessment for AEs at each visit and record the event on the appropriate AE eCRF. Any SAE that occurs from the time of ICF through 30 days following the last dose of study drug should be reported to the Sponsor per [Section 10.2.7.4](#).

Wherever possible, a specific disease or syndrome rather than individual associated signs and symptoms should be identified by the Investigator and recorded on the eCRF. However, if an observed or reported sign or symptom is not considered a component of a specific disease or syndrome by the Investigator, it should be recorded as a separate AE on the eCRF. Additionally, the condition that led to a medical or surgical procedure (eg, surgery, endoscopy, tooth extraction, transfusion) should be recorded as an AE, not the procedure.

Any medical condition already present at screening or baseline should not be reported as an AE unless the medical condition or signs or symptoms present at baseline changes in severity or seriousness at any time during the study. In this case, it should be reported as an AE.

Clinically significant abnormal laboratory or other examination (eg, ECG) findings that are detected during the study or are present at baseline and significantly worsen during the study should be reported as AEs. The Investigator will exercise his or her medical and scientific judgment in deciding whether an abnormal laboratory finding or other abnormal assessment is clinically significant. Significant abnormal laboratory values occurring during the clinical study will be followed until repeat tests return to normal, stabilize, or are no longer clinically significant. Any abnormal test that is determined to be an error does not require reporting as an AE.

Each AE is to be evaluated for duration, severity, seriousness, and causal relationship to the investigational drug. For each AE, the following information will be recorded:

- Description of the event (eg, headache)
- Date of onset
- Date of resolution (or that the event is continuing)
- Action taken as a result of the event
- Seriousness of the event
- Severity of the event
- Outcome of the event

- Investigator's assessment of relationship to study drug.

A cluster of signs and symptoms that results from a single cause should be reported as a single AE (eg, fever, elevated WBC, cough, abnormal chest x-ray, etc, can all be reported as "pneumonia").

The Investigator will carefully evaluate the comments of the patient and the response to treatment in order that he/she may judge the true nature and severity of the AE. The question of the relationship of AEs to study drug administration should be determined by the Investigator or study physician after thorough consideration of all facts that are available.

Additional information will be collected regarding muscle-related AEs that may include, but may not necessarily be limited to, a muscle-related questionnaire, with questions regarding type of muscle-related symptoms, location of the muscle-related AE, and potential cause of the muscle-related AE.

10.2.4. Severity of Adverse Events

It is the Investigator's responsibility to assess the intensity (severity) of an AE.

The severity of the AE will be characterized as mild, moderate, or severe according to the following definitions:

- Mild: Events are usually transient and do not interfere with the patient's daily activities
- Moderate: Events introduce a low level of inconvenience or concern to the patient and may interfere with daily activities
- Severe: Events interrupt the patient's usual daily activity, are incapacitating with inability to do usual activities, or significantly affect clinical status and warrant intervention and/or close follow-up

Note: A severe AE need not be serious and an SAE need not, by definition, be severe.

10.2.5. Relationship

Medical judgment should be used to determine the cause of the AE considering all relevant factors such as, but not limited to, the underlying study indication, coexisting disease, concomitant medication, relevant history, pattern of the AE, temporal relationship to the study medication, dechallenge or rechallenge.

It is the Investigator's responsibility to assess the relationship between the study drug and the AE. The degree of "relatedness" of the AE to the study drug may be described using the following scale:

- Not Related: No temporal association and other etiologies are likely the cause
- Unlikely: While cannot be definitively ruled as not related to IMP, a causal association is remote, and other etiologies are more likely to be the cause. For reporting and summarization, events assessed as "Unlikely" to be related to IMP will be considered as "Not Related" to IMP for regulatory reporting purposes.

- Possible: Temporal association, but other etiologies are likely the cause. However, involvement of the study drug cannot be excluded.
- Probable: Temporal association, other etiologies are possible but unlikely. The event may respond if the study drug is discontinued.
- Definite: Established temporal association with administration of the study drug with no other more probable cause. Typically, the event should resolve when the study drug is discontinued and recur on re-challenge.

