10.2.7.5. Reporting of Serious Adverse Events to Regulatory Authorities

The Sponsor (and/or designee) is responsible for submitting expedited reports of suspected and unexpected serious adverse reactions (SUSARS) to the appropriate regulatory authorities. All Investigators participating in ongoing clinical studies with the study drug will be notified by the Sponsor (or designee) of SUSARS. SUSARS must be communicated as soon as possible to the appropriate IRB/IEC by the investigator, as applicable and/or reported in accordance with local laws and regulations. Investigators should provide written documentation of IRB/IEC notification for each report to the Sponsor.

SAEs that are anticipated to occur in this patient population will be collected and reported by the Investigator as described in [Section 10.2.7.4](#). However, these events will not be submitted to the regulatory authorities as expedited reports unless they meet SUSAR criteria. These events that are considered to be exempt from expedited reporting include the following clinical endpoints:

- CV death
- Nonfatal MI
- Nonfatal stroke
- Unstable angina requiring hospitalization
- Coronary revascularization
- Heart failure requiring hospitalization
- Noncoronary arterial revascularization

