##### 19.1.1.2. Relationship to Study Medication

Relationship to IMP, as indicated by the Investigator, is “not related” if the TEAE is “not related” or “unlikely”. A “related” TEAE is defined as a TEAE with a relationship of “possibly related”, “probably related”, or “definitely related” to study medication. TEAEs with a missing relationship

Version Number: 1.7  
 Version Date: 21Mar2018

to study medication will be regarded as "probably related" to study medication. If a patient reports the same AE more than once within that SOC/ PT, the AE with the worst case relationship to study medication will be used in the corresponding relationship summaries.

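### Protocol 10.2.2 and 10.2.5 set conflicting causality thresholds for events rated Unlikely, and SAP 19.1.1.2 builds its related-event tables on the cut in 10.2.5

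*Protocol*

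**What the plan says.** - **Protocol 10.2.2** treats a response as an adverse drug reaction (ADR) when the causal relationship "between a medicinal product and an AE is at least a reasonable possibility (ie, the relationship cannot be ruled out").
- **Protocol 10.2.5** gives a five-level scale: Not Related, Unlikely, Possible, Probable, Definite. The second level reads "Unlikely: While cannot be definitively ruled as not related to IMP, a causal association is remote", with other causes judged more likely. The section then adds the rule that "events assessed as 'Unlikely' to be related to IMP will be considered as 'Not Related' to IMP for regulatory reporting purposes", and says the rule also serves summarization.
- **Protocol 10.2.7.5** makes the sponsor responsible for "expedited reports of suspected and unexpected serious adverse reactions (SUSARS"). A list of anticipated clinical endpoints is exempt unless the event meets those same criteria.
- **Protocol 10.2.7.4** sends every SAE to the safety designee within 24 hours, whatever its causality rating, from consent to 30 days after the last dose. Later than that, 10.2.7.4, 10.2.9 and 10.2.10 require only related SAEs.
- **SAP 19.1.1.2** works from the site's rating ("Relationship to IMP, as indicated by the Investigator, is" is how the rule opens). The two lowest levels become not related and the three highest become related. A missing rating is counted as probably related.
- **SAP 19.1.1, 19.1.3 and Appendix 3** use that split for summaries by relationship, for serious related TEAEs, and for DMC tables 14.3.1.4 (related TEAEs) and 14.3.1.5 (related serious TEAEs).

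**The concern.** A safety plan needs one answer to the question of when an event counts as a suspected reaction. Here there are two. Section 10.2.2 sets the bar at failure to rule the drug out. Section 10.2.5 describes a class of events for which the drug has not been definitively ruled out, and files that class on the unrelated side.

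Two things depend on which section governs. The first is whether a serious, unexpected event is considered for expedited reporting. The second is what the related-event tables contain, including those the DMC sees. If sites and the sponsor read the sections differently, the same clinical picture could be handled differently from one site to the next, and nothing in the text would show which handling was intended.

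**Working it through.** No arithmetic applies: the plan states no figure on this point and gives no event counts. The check sets the definitions side by side and follows one event through them.

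**1. The levels around the cut (Protocol 10.2.5)**

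| Level | Timing | Other causes | Drug excluded? | Side of the cut |
|---|---|---|---|---|
| Not Related | no temporal association | likely | not stated | not related |
| Unlikely | not stated | more likely | not definitively; association remote | not related |
| Possible | temporal association | likely | no | related |

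The sources for the outer rows are "Not Related: No temporal association and other etiologies are likely the cause" and "Possible: Temporal association, but other etiologies are likely the cause. However, involvement of the study drug cannot be excluded".

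**2. Against 10.2.2.** The parenthesis in 10.2.2 begins with ie, so it restates the main phrase and does not add a separate condition. On that reading an ADR is any event whose relationship has not been ruled out. The Unlikely row has not been definitively ruled out, so it meets the parenthesis, yet 10.2.5 puts it on the not-related side. The two sections disagree about the same row.

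**3. A gap beside the conflict.** Not Related requires that there be no temporal association. An event that follows dosing but plainly has another cause does not fit that level. The nearest place for it is Unlikely. That level can therefore hold two kinds of event, those effectively excluded and those not excluded, and both are mapped the same way.

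**4. One event followed through.** Take an SAE that is unexpected and rated Unlikely.
- Under 10.2.2, read literally, it can be an ADR.
- Under 10.2.5 it is Not Related for regulatory purposes, so it may not be taken as a suspected reaction under 10.2.7.5. Neither document describes a sponsor causality assessment that could override the site's rating.
- Under SAP 19.1.1.2, if treatment-emergent, it is absent from tables 14.3.1.4 and 14.3.1.5.
- If it occurs after the 30-day window, it need not be reported to the sponsor.

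**5. What still captures it.**
- Up to 30 days after the last dose it reaches the safety designee within 24 hours regardless of rating (10.2.7.4).
- If treatment-emergent, it stays in the all-TEAE and serious-TEAE summaries (SAP 19.1.1 and 19.1.3).
- The DMC sees it in tables 14.3.1.1 to 14.3.1.3 and, where applicable, in 14.3.1.6 (discontinuations) and 14.3.1.8 (events of special interest).

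**The case against.** The best defence is that the operative test in 10.2.2 is reasonable possibility, that the parenthesis is only a gloss, and that an association called remote falls below a reasonable possibility. Failing to rule something out definitively is also a weaker statement than failing to rule it out. This is a sensible reading and may be what was meant. It does not remove the conflict, because the protocol itself equates the two phrases, and the defence works only if that equation is dropped or reworded.

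A reader might infer that Unlikely and Possible are interchangeable. They are not: only Possible requires a temporal association, and only Unlikely calls the association remote. The boundary is soft, but it exists.

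A reader might also infer that every SAE rated Unlikely escapes expedited reporting. The documents do not support that. The event must also be unexpected, and expedited submission is the sponsor's task, with the SAE already in hand if it fell within the 30-day window. An SAE before double-blind dosing is not a TEAE, so it could not have entered the related-TEAE tables in any case.

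Finally, a reader might infer that harm is understated overall. The safety endpoint in 5.2.4 is TEAE incidence whatever the cause, in a randomized, double-blind comparison, and those tables lose nothing. The SAP's treatment of missing ratings as related also works in the cautious direction.

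**Conclusion.** The conflict is in the current text and should be corrected. Its reach is narrow:
- the classification, and possible expedited handling, of events that are serious, unexpected and rated Unlikely;
- the content of the related-event summaries;
- SAEs rated Unlikely after the 30-day window.

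No event is removed from the all-cause TEAE or SAE tables, and the primary safety comparison is untouched. The number of events concerned cannot be derived, because the documents give no count and no expected frequency of Unlikely ratings.

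The conclusion rests on two assumptions: that the parenthesis in 10.2.2 means what it literally says, and that no sponsor causality review outside these documents settles the matter. If remote was meant to fall below a reasonable possibility, the fault is one of wording only, but the sections must still be reconciled.

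**What to change.** Bring 10.2.5 into line with 10.2.2, so that one threshold governs both reporting and tables:

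1. Define Unlikely as an event whose relationship to IMP has been assessed and is considered ruled out by another identified cause, even if the event follows dosing.
2. State that any event whose relationship to IMP cannot be ruled out is rated at least Possible.

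The mapping of Unlikely to Not Related, and SAP 19.1.1.2, then stand unchanged. Post-dose events with a clear other cause also gain a proper level.

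The cost is two sentences in 10.2.5, matching eCRF completion guidance, and somewhat more events counted as related.

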10.2.6. Monitoring and Follow-up of Adverse Events

Patients having AEs will be monitored with relevant clinical assessments and laboratory tests, as determined by the Investigator. All follow-up results are to be reported to the Sponsor personnel or the authorized Medical Monitor. Any actions taken and follow up results must be recorded either on the appropriate page of the eCRF or in appropriate follow-up written correspondence, as well as in the patient's source documentation. Follow-up laboratory results should be filed with the patient's source documentation.

For all AEs that require the patient to be discontinued from the study, relevant clinical assessments and laboratory tests must be repeated at appropriate intervals until final resolution, stabilization of the event(s), or until the patient is lost to follow-up or dies.

Patients with AEs that are ongoing at study completion or study withdrawal must be followed until resolution or for 30 days after the last study visit, whichever comes first (see [Section 8.3](#)).

10.2.7. Treatment-Emergent Adverse Event

TEAE are defined as AEs that begin or worsen after the first dose of study drug.

10.2.7.1. Definition of Serious Adverse Event

An SAE is defined as any AE occurring at any dose that results in any of the following outcomes:

- Results in death
- Is life threatening
- Requires in-patient hospitalization or prolongation of existing hospitalization
- Results in persistent or significant disability/incapacity, or substantial disruption of the ability to conduct normal life functions
- Is a congenital anomaly/birth defect
- An important medical event

NOTE: Hospitalization is defined as a formal inpatient admission. This will not include admissions under "23-hour Observational Status", an Emergency Room visit without hospital admission or an Urgent Care visit and therefore, such events will not be recorded as an SAE under this criterion, nor will hospitalization for an elective or outpatient procedure scheduled or planned before signing of informed consent. However, unexpected complications that occur

during elective or outpatient surgery should be recorded as AEs and assessed for seriousness. Admission to the hospital for social or situational reasons (eg, no place to stay, live too far away to come for hospital visits) will not be considered inpatient hospitalizations.

Important medical events that may not result in death, be life threatening, or require hospitalization may be considered an SAE when, based upon appropriate medical judgment, they may jeopardize the patient and may require medical or surgical intervention to prevent one of the outcomes listed in this definition. Examples of such medical events include allergic bronchospasm requiring intensive treatment in an emergency room, blood dyscrasias, convulsions that do not result in inpatient hospitalization, or the development of drug dependency or drug abuse.

Any clinical endpoints that meet SAE criteria will be reported as SAEs. The CEC will adjudicate clinical endpoints in a blinded fashion, but the DMC will review clinical endpoints and SAEs in an unblinded fashion.

10.2.7.2. Definition of Serious Adverse Event Events or Outcomes not Qualifying as Serious Adverse Events

The following are not considered SAEs and therefore do not need to be reported as such:

- Preplanned or elective hospitalization including social and/or convenience situations (eg, due to inclement weather)
- Overdose of either Esperion study drug or concomitant medication unless the event meets SAE criteria (eg, hospitalization). However, the event should still be captured as a nonserious AE on the appropriate eCRF page

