**19.1.3. SERIOUS ADVERSE EVENTS**

Serious adverse events (SAEs) are those events recorded as 'serious' on the adverse events page of the eCRF. Summaries of serious TEAEs and serious related TEAEs by SOC and PT will be prepared.

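### An elective inpatient admission arranged after consent for a new or worsened condition is an SAE under Protocol 10.2.7.1 but not under 10.2.7.2

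*Protocol*

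**What the plan says.** Protocol 10.2.7.1 starts from the adverse event: "An SAE is defined as any AE occurring at any dose that results in any of the following outcomes". One of the outcomes is "Requires in-patient hospitalization or prolongation of existing hospitalization". A note under the list adds that "Hospitalization is defined as a formal inpatient admission". The same note removes several things from this criterion: 23-hour observation stays, emergency room visits that do not lead to admission, and urgent care visits. On elective admissions it continues: "nor will hospitalization for an elective or outpatient procedure scheduled or planned before signing of informed consent". It also removes "Admission to the hospital for social or situational reasons (eg, no place to stay, live too far away to come for hospital visits".

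Protocol 10.2.7.2, the next section, lists what does not count as an SAE and need not be reported as one. Its first bullet is "Preplanned or elective hospitalization including social and/or convenience situations (eg, due to inclement weather". Nothing in the bullet refers to consent or to any other date. The second bullet, on overdose, keeps an exception for an event that otherwise meets the SAE criteria. The first bullet has no such exception.

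SAP 19.1.3 adds no rule of its own: "Serious adverse events (SAEs) are those events recorded as 'serious' on the adverse events page of the eCRF".

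**The concern.** Two adjacent sections of current text set different limits for the same kind of event. In 10.2.7.1 the elective exemption depends on when the procedure was planned. In 10.2.7.2 being elective is enough, because the bullet joins preplanned and elective with an or.

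The gap concerns events that matter in this trial. The protocol enrolls patients with coronary, peripheral and cerebrovascular disease (6.2.1), and exclusion 4 in 6.2.2 keeps out patients who already plan a major surgical or interventional procedure. An elective inpatient revascularization during the treatment period would therefore normally have been arranged after consent, which is exactly where the sections disagree.

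At stake is the consistency of the SAE count across approximately 71 sites, and whether a qualifying event is reported within 24 hours (10.2.7.4). Safety over 24 weeks compared with placebo is a secondary objective (5.1.2).

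**Working it through.** No figure in the plan bears on this point, so the check is a comparison of text.

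**Inputs.** The SAE definition and its note (Protocol 10.2.7.1); the exclusion list (10.2.7.2); the rules for what is recorded as an AE (10.2.3); the SAP's rule for identifying SAEs (SAP 19.1.3).

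**Step 1: is there an AE?** Under 10.2.3, a condition already present at screening or baseline is not an AE unless it changes during the study. The condition that led to a procedure is what gets recorded, not the procedure. So an AE exists when the condition behind the admission is new or has worsened.

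**Step 2: apply the hospitalization criterion under each section.**

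| Admission | Under 10.2.7.1 | Under 10.2.7.2 | Agree? |
|---|---|---|---|
| Elective procedure planned before consent | Not an SAE | Not an SAE | Yes |
| Social or situational admission | Not an SAE | Not an SAE | Yes |
| Elective admission after consent, pre-existing condition unchanged | No AE, so not an SAE | Not an SAE | Yes |
| Elective inpatient admission arranged after consent, new or worsened condition | SAE | Not an SAE | **No** |

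The conflict is confined to the last row. The other exemptions in 10.2.7.1 (observation stays, emergency room and urgent care visits) do not reach it, because it involves a formal inpatient admission. Nor does that section's sentence on unexpected complications of elective surgery, which concerns the complication and not the condition that led to the admission.

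**Step 3: does anything break the tie?** Neither section refers to the other on this point, and no statement of precedence was found. Protocol 11.1 lets the SAP override the protocol on data analysis, but SAP 19.1.3 simply takes the site's entry.

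**Step 4: what changes downstream?** Changed: the serious flag on the AE page, the 24-hour report under 10.2.7.4, the serious-TEAE summaries under SAP 19.1.3, and the DMC's Tables 14.3.1.3 and 14.3.1.5 (SAP Appendix 3). Unchanged: the AE record itself, the all-TEAE tables (SAP 19.1.1), and the adjudication and tabulation of clinical endpoints (Protocol 10.4, SAP 19.3).

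**The case against.** The best defense is that the 10.2.7.2 bullet is shorthand. It sets elective beside preplanned and beside social and convenience situations, with bad weather as its example, so it may be meant only to repeat the exemptions of 10.2.7.1. That reading is possible, and a careful site might adopt it. It is not what the words say, and the overdose bullet shows that the list states a deferral to the SAE criteria where one is intended.

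Several further points stand and limit the finding:

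- **No event is lost.** A reader might infer that these events drop out of the safety data. They do not: the AE stays recorded and only its serious flag is in doubt. The important-medical-event criterion in 10.2.7.1 could also make some of them serious on another ground, though that rests on case-by-case judgment and does not reconcile the two rules.
- **Revascularizations have their own route.** A reader might infer that the cardiovascular results depend on this. Coronary and non-coronary revascularizations are adjudicated by the blinded CEC (Protocol 10.4) and tabulated as clinical endpoints (SAP 19.3). Coronary revascularization is a MACE component, and the DMC receives investigator-reported and adjudicated MACE tables (14.3.1.15 and 14.3.1.16).
- **Section 10.2.7.5 does not settle it.** That section lists "Coronary revascularization" and other clinical endpoints, which might be taken to show that every revascularization is an SAE. The list names events exempt from expedited regulatory reporting unless they meet SUSAR criteria. The operative sentence, in 10.2.7.1 and 10.4, has clinical endpoints reported as SAEs only when they meet the SAE criteria, which is the question left open.
- **No bias between arms is shown.** Site personnel are blinded (Protocol 6.3), SAP 19 plans no between-group tests on safety data unless specified, and no efficacy analysis uses SAE status.

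**Conclusion.** The contradiction is real and lies in current text, but it is narrow. It affects formal inpatient admissions that are elective, were arranged after consent, and follow from a new or worsened condition. For those, the hospitalization criterion is met under one section and set aside under the next.

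The size is unknown. The documents give neither an SAE rate nor the share of SAEs that are elective admissions. A reader might infer that a sizeable fraction of the SAE count is at risk, but any such fraction would only return the share assumed at the start. The number of patients is probably small. That judgment, and the view that the effect should not favor an arm, rest on the narrowness of the category and on blinding being maintained.

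It should still be corrected. As written, a site that follows 10.2.7.2 to the letter can leave a qualifying SAE unreported within 24 hours and out of the serious-TEAE tables, while another site following 10.2.7.1 reports the same event.

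**What to change.** Reconcile the two sections by limiting the first bullet of 10.2.7.2 to the exemptions already in 10.2.7.1: admission for a procedure scheduled or planned before the patient signed consent, and admission for social or situational reasons. The condition behind any other elective inpatient admission is then assessed for seriousness in the usual way.

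Tell sites which rule applies, and have them re-check AEs that were entered as non-serious only because the admission was elective. The re-check should be done without knowledge of treatment assignment. SAP 19.1.3 can stay as it is, since it will then rest on one definition.

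The cost is a short protocol amendment under 16.3, a clarification to approximately 71 sites, and a query limited to AEs with an elective admission. A few more SAE reports may follow, so the reported SAE percentage could rise slightly in both arms.
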